14.7 Participants who lose capacity during the study

In the unlikely event that the participant loses capacity to consent during the study, the participant would be withdrawn from the study. Identifiable data already collected with consent would be retained and used in the study. No further data would be collected, or any other research procedures carried out on or in relation to the participant.

15 RANDOMISATION

15.1 Timing of randomisation

The patient will be randomised after consent and baseline data have been obtained, either in the emergency department, or in a fracture clinic (face-to-face or virtual clinic- if virtual, site will inform the parent/guardian of the treatment allocation). All hospital treatment areas have access to the internet so will access the randomisation service in real time, i.e. there will be no delay to patient treatment.

15.2 Randomisation procedure

Randomisation should take place once informed consent has been given. Eligibility will be reconfirmed at randomisation. Participants will be randomised by the site research team via the ODD SOCKS REDCap study database.

Participants will be randomised to one of the following treatment arms:

Arm	Treatment
Surgical Reduction (intervention)	Surgical Reduction with or without fixation. The bones will be realigned under general anaesthesia or sedation altering the conscious state of the child.
Conservative Treatment (usual care/comparator/control arm)	Application of a plaster cast to hold the bone fragments in the optimal position without giving medication to deliberately alter the conscious level of the child.

Upon randomisation of a participant the central CTU study team and a member of the site research team will be notified by an automated email.

Full details of the randomisation procedure will be stored in the Randomisation and Blinding Plan in the confidential statistical section of the TMF.

15.3 Randomisation methodology

Participants will be randomly allocated to the treatment options via automated, secure (encrypted), web-based randomisation provided by the Oxford Clinical Trials Research Unit (OCTRU) using a REDCap platform. Minimisation will be implemented with a 1:1 allocation ratio using the REDCap-Minimization module (ref GitHub - Nottingham-CTU/REDCap-Minimization: REDCap External Module: Perform minimization.) Allocation will be minimised to ensure balance for:

- biological sex
- participant age group (8-12 years, 13-15 years)
- emergency realignment performed

The first few participants will be randomised using simple randomisation, to seed the minimisation algorithm, and a non-deterministic probabilistic element will be included to prevent predictability of treatment allocation. The randomisation schedule will be designed by the OCTRU trial statistician and full details will be detailed in the randomisation and blinding plan.

15.3.1 Justification for stratification factors

Stratification by biological sex will ensure balance because males have better remodelling capacity than females of the same age during childhood, owing to different rates of skeletal maturation.

Stratification by participant age will ensure balance, because although younger children have better remodelling capacity than older children, they also have more growth remaining and therefore more time for deformity to develop if the growth plate is damaged.

Stratification considering whether emergency realignment was performed will ensure that magnitude of initial deformity is captured. In some instances, the fracture needs emergency realignment to avoid damage to skin, blood vessels or soft tissues. Once all emergency procedures are completed, the fracture position may be assessed against the criteria for inclusion.

15.4 Back-up randomisation procedure

There is no back-up randomisation procedure for this study.

16 SUB-STUDIES/TRANSLATIONAL STUDIES/MECHANISTIC STUDIES

There are currently no planned sub-studies, translational studies, or mechanistic studies.

17 STUDY ASSESSMENTS/PROCEDURES AND DATA COLLECTION

The study flow chart can be found in Appendix 1 of this protocol.

17.1 Overview

Participants and/or their parents will be asked to complete a set of baseline questionnaires after providing consent, but prior to being allocated one of the two study treatments. Table 2 shows participant data collection time points.

After the allocated treatment has been provided, the research team will complete a treatment form. Follow-up clinical data (i.e., routine records check related to planned and unplanned care) will be collected at 8 weeks, 12 months, and 24 months post-randomisation (see Table 3).

17.2 Study questionnaires

Questionnaires will generally be self-reported, however parent input will be advised when completing the satisfaction with care, resource use and complication questionnaires. Questionnaires will be sent via email/text to parents, and children over 12 if they agreed to be contacted. Refer to section 10.3.

17.3 Data Collection

Baseline clinical and complication data will be completed during the primary and routine follow-up clinical appointment (8 weeks) by the recruiting team. For participant data, an advance notification will be sent when questionnaires are due and then the parent and/or child will be prompted to complete questionnaires at 6 weeks, 3 months, 6 months, 12 months, and 24 months.

17.3.1 Baseline

Table 1 Baseline Data Collection

Data sourced/collected by site research team	Data directly reported by participants (patient-reported outcomes)
Trial intervention (Treatment CRF)	PROMIS Mobility (Primary Outcome)
	EQ-5D-Y
	Wong Baker FACES Pain Score

17.3.2 Follow-up assessments/subsequent visits

Follow-up questionnaires will be sent to parents at 6 weeks, 3 months, 6 months, 12 months and 24 months. Details of Participant CRFs collected at each time point are described in Table 2 below.

Table 2 Participant Data Collection time points

Procedures	Screening	Baseline	6 weeks	3 months	6 months	12 months	24 months
Informed Consent +/- Assent	Х						
Demographic Data	Х						
PROMIS Mobility (Primary Outcome at 24 months)		Х	Х	Χ	Х	Х	х
EQ-5D-Y / Wong Baker FACES Pain Score		х	Х	Х	Х	х	Х
Resource use			Х	Х	Х	х	Х
Educational Participation			Х	Х	Х		
VAS Cosmesis/ Satisfaction with care				Х		Х	Х
Additional Care CRF (Complications)			Х			Х	Х

Participants will usually attend orthopaedic follow-ups as part of standard care until at least 2 years after the initial assessment, to monitor for signs of growth disturbance. During these visits, the clinical team will perform a clinical assessment and a radiographic examination will normally occur. At all clinic visits, the research team will record any complications that have occurred.

Table 3 Site Data Collection time points

Procedures	Screening (clinic/virtual clinic)	Baseline (clinic/virtual clinic)	8 weeks clinic	12 month clinic	24 month clinic
Assessment of Eligibility Criteria (Screening log)	Х				
Informed Consent +/- Assent	Х				
Trial intervention (Treatment CRF)		Х			
Week 8 Follow Up Immobilisation CRF			Х		
Site Follow Up Complications CRF			Х	Х	Х
Study Measurements: Leg Length Discrepancy				Х	Х
Radiographs					Х

17.4 Communication with study participants by the central CTU study team

Participants will be notified to complete study questionnaires by e-mail and/or text message if they are over 12 years old and agreed to be contacted, otherwise questionnaires will be sent to the parent. Parents/participants may be sent reminder messages and where possible may be asked to complete questionnaires during a routine clinic visit. Participants that do not complete their study questionnaires may be telephoned to collect the data or request return of the questionnaire. Parents/participants will receive an initial e-mail/and or text message and reminder messages by a member of the central CTU study team to collect outcome data. A welcome letter will be sent out to participants upon recruitment into the study, as well as a reminder postcard at 12 and 24 months.

17.5 Qualitative assessments

No qualitative research will be performed as part of the study.

17.6 Withdrawal

Withdrawal of consent means that a participant (and/or their parent) has expressed a wish to withdraw from the study altogether or from certain aspects of the study only. The type of withdrawal will be collected on the CRF labelled 'Withdrawal'.

Participants may also be withdrawn from the study (or aspects of the study) by their clinician if they believe the participant needs to be withdrawn.

The Withdrawal CRF should be completed to document the reasons for withdrawal and state who the decision to withdraw was made by. Discussions and decisions regarding withdrawal should be documented in the participant's medical notes. Investigators should continue to follow- up any SAEs and should continue to report any SAEs to resolution in the CRF in accordance with the safety reporting section.

Where a participant expresses a wish to withdraw from the study, the research team will determine which aspect(s) of the study the participant wishes to withdraw from.

The aspects of the study that the participant may request to withdraw from are as follows:

- No longer willing to complete study questionnaires
- No longer willing to complete study questionnaires AND have routine data from the medical record provided to the study

Where a participant wishes to withdraw from all aspects of study participation detailed above, this will be recorded on the Withdrawal CRF as full withdrawal.

Participants (or their parents) may decline to continue to take part in the trial at any time without prejudice. A decision to decline consent or withdraw will not affect the standard of care the participant receives. Participants (or their parents) can withdraw by contacting the research team, using the contact details found on patient information materials and the trial website. Participants (or their parents) will **not** have the option to withdraw the data collected up until the point of withdrawal, as the data will be required for the intention-to-treat (ITT) and safety analysis. The options for withdrawal will be explained clearly in the PIS. The type of withdrawal and reason for withdrawal, if the participant is willing to provide one, will be recorded in the withdrawal CRF. Contact details for these participants will be destroyed. Withdrawn participants or participants deemed ineligible after randomisation will not be replaced.

Completion of the Withdrawal CRF by the site research team will trigger a notification to the Central CTU study team. Appropriate action will be taken by the study teams (centrally at the CTU and by the site research team at each participating site) to ensure compliance with the participant's withdrawal request. This may include marking future CRFs as not applicable and ensuring any relevant communications which the participant had consented to receive regarding their participation are no longer sent.

18 BLINDING AND CODE BREAKING

18.1 Blinding

Participants and their parents cannot be blinded to their treatment. The treating clinician also cannot be blinded to the treatment they are providing. The outcome data will be collected directly from the patient and their parents.

The CI, Trial Management Group (TMG) and Trial Statistician will not be blinded.

Outcome assessors will be blinded to the participant's treatment allocation. For outcomes that could potentially be affected by bias (i.e. primarily radiographic measurements), an independent panel of experienced orthopaedic surgeons, blinded to the intervention where feasible (i.e. no metalwork), will review and interpret the radiographs.

18.2 Code break/ unblinding

Not applicable for this study.

19 SAMPLES

This study protocol does not involve any taking of new biological samples or any use of pre-existing samples.

20 SAFETY REPORTING

20.1 Safety reporting period

Safety reporting for each participant will begin from the first point of administration of the intervention and will end when the participant has reached their final main follow up time point, at 24 months post-randomisation. This is a low risk, pragmatic trial where both trial interventions are in

common use. Considering this, we do not anticipate many serious adverse events (SAEs) associated with either treatment.

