13 STUDY INTERVENTION AND COMPARATOR

All of the hospitals involved in this study are familiar with both study treatment techniques. All patients will initially receive temporary immobilisation and analgesia at the discretion of the treating clinician, as per any local or national guidelines (i.e. Royal College of Emergency Medicine best practice guidelines for the management of acute pain in children).²⁶ Randomisation will occur at the point where the treating clinician believes that the child would benefit from surgical reduction with or without fixation.

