13.1 Surgical Reduction (intervention)

Surgical reduction with or without fixation will be performed. The bones will be realigned under general anaesthesia or sedation altering the conscious state of the child. It may be possible to achieve realignment without making a skin incision, or an incision may be required. The need for an incision, type and position of incision and method used to hold the bones in position will be at the discretion of the clinician; i.e. plaster cast alone, plaster cast and screws/wires, plaster cast and plate and screws. A record will be made of the operative details, the cast details and any cast changes. Following surgery, usual practice is for the leg to be immobilised in cast for 4-6 weeks. Specific details on the techniques and materials used in theatre will be collected for each participant.

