13.2 Conservative Treatment (usual care/comparator/control)

This technique involves the application of a plaster cast to hold the bone fragments in the optimal position without giving medication to deliberately alter the conscious level of the child. This may be the initial plaster cast used to stabilise the fracture, or the plaster cast may be changed by the clinician to maximise patient comfort and fracture stability. Although the principles of applying a plaster cast are inherent in the technique, in this pragmatic trial the type of casting material, extent of the cast and the details of the technique will be left to the discretion of the treating clinician as per their usual practice. A record will be made of the cast details and any changes. Usual practice is for the plaster cast to be used for 4-6 weeks.

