22.4 Inclusion in analysis

The principal analysis will be performed on the as randomised (ITT) population, analysing participants with available outcome data in their randomised groups, regardless of adherence or actual treatment received. The study will be reported in line with CONSORT guidelines.

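### Section 20.1 starts safety reporting at the intervention, not at randomisation, so the stated window can open later in the surgical arm

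*Protocol*

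**What the plan says.** Section 20.1 fixes the two ends of the safety-reporting period by different events. It opens with treatment: "Safety reporting for each participant will begin from the first point of administration of the intervention". It closes by reference to randomisation: it "will end when the participant has reached their final main follow up time point, at 24 months post-randomisation".

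The treatment definitions set when that opening falls in each arm.

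- Before definitive care (section 13): "All patients will initially receive temporary immobilisation and analgesia at the discretion of the treating clinician".
- Randomisation (section 15.1): "The patient will be randomised after consent and baseline data have been obtained, either in the emergency department, or in a fracture clinic".
- Conservative arm (section 13.2): "This may be the initial plaster cast used to stabilise the fracture, or the plaster cast may be changed by the clinician".
- Surgical arm (section 13.1): "The bones will be realigned under general anaesthesia or sedation altering the conscious state of the child".

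The comparative sections use randomisation. Section 9.3 lists the complication rate among outcomes compared over the two years from randomisation. Section 22.3.2 analyses the proportion of participants with at least one complication. Section 22.4 sets the principal analysis as randomised, "analysing participants with available outcome data in their randomised groups, regardless of adherence or actual treatment received".

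**The concern.** A comparison of randomised groups should count events from a point that is the same in both arms and is not affected by allocation. Randomisation is such a point; the start of treatment is not. Here a conservative-arm child whose first cast is kept is inside the window from randomisation, or on a literal reading even before it. A surgical-arm child is also immobilised but enters the window only when the reduction takes place. Section 20.3 names cast complications, including pressure areas, as foreseeable in either group. The same cast problem on the same day after randomisation could therefore be inside the stated window in one arm and outside it in the other.

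A second gap concerns adherence. The analysis keeps every child in the randomised group, but section 20.1 does not say when the window opens for a child allocated to surgery who does not have it. This is foreseeable, since section 22.2 itself reports strong parental anxiety about surgery.

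At stake is a clear rule for which events count, both for the complication comparison and for the safety data that the DSMC reviews (section 25.4.2). That review matters here because section 22.6.1 sets no formal stopping rules.

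**Working it through.** **The protocol's own figure.** The only design figure is the sample size in section 22.2, and this point does not depend on it. For a difference of 5, SD 10, two-sided 5% and 90% power, the two-sample t-test needs 85.03 per arm, which rounds up to 86 (172 in total); power at 86 per arm is 0.903. Allowing for 10% attrition, 172 / 0.9 = 191.1, rounded up to 192. The stated figures reproduce and would not change under the fix.

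**When the stated window opens, by situation.**

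- Conservative arm, first cast kept: at or before randomisation, so no time is lost.
- Conservative arm, cast changed: possibly at the change, which may follow randomisation.
- Surgical arm, reduction performed: at the reduction, after randomisation.
- Surgical arm, reduction not performed: not stated.

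**What captures an event between randomisation and surgery.**

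- Pointing to capture: section 9.3 counts complications from randomisation, and section 17.3.2 has the research team record any that have occurred at every clinic visit. Neither ties the start to treatment.
- Pointing away: the complications paragraph of section 9.3 limits recording to complications of the intervention, and section 20.1 opens the safety window only at treatment.
- Shared forms: section 20.6 collects safety events on the Additional Care and Site Follow Up Complications forms, which also supply the complication outcome in section 9.3. One pair of forms therefore serves two starting points.

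A site following the first set of passages would record a pre-surgery event. A site following the second could reasonably leave it out.

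**Size of the window difference.** The protocol gives no time from randomisation to surgery. The 7-day limit in section 11.4 is the age of the injury at entry, not a wait for surgery. Let *d* be an assumed wait in days. The share lost in the surgical arm is *d* / 730 of the 24 months and *d* / 42 of the first six weeks, the upper end of the usual cast period in sections 13.1 and 13.2.

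- *d* = 0: 0% and 0%
- *d* = 1: 1/730 = 0.14%; 1/42 = 2.4%
- *d* = 3: 3/730 = 0.41%; 3/42 = 7.1%
- *d* = 7: 7/730 = 0.96%; 7/42 = 16.7%
- *d* = 14: 14/730 = 1.92%; 14/42 = 33.3%

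These are shares of time, not of events. No event rate for this interval is given, so they cannot be turned into a number of events.

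**The case against.** The strongest reply is that section 20.1 governs safety reporting, not the comparative outcome. The complication rate has its own common window in section 9.3, and nothing in sections 9.3, 17.3.2 or 22.3.2 refers back to section 20.1. Cast problems are foreseeable events, and section 20.4 sends them to the complication forms, so they can be recorded whenever they occur. What remains for section 20.1 to exclude is narrow: sections 20.4 and 20.7 confine reporting to serious events related to the intervention or to research procedures, and few events before an operation could be attributed to it. Some conservative-arm children will have a cast change after randomisation, so their window may also open late. A child allocated to surgery and treated in a cast has arguably received a trial treatment, which could be taken as the start.

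Most of this stands. A reader might infer from section 20.1 that surgical-arm events before the operation go uncounted, or that the complication comparison is biased in favour of surgery. The documents do not support either inference, because the comparison is defined from randomisation and its forms can capture those events. Nor do they support a figure for missing events, since both the wait and the event rate would have to be assumed.

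The reply does not remove the inconsistency. The limit to complications of the intervention and the use of the same forms for both purposes leave a site without a clear instruction. Section 20.1 still does not state the start for a child who does not receive the allocated surgery.

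**Conclusion.** The point holds as a minor inconsistency. The safety-reporting window in section 20.1 depends on treatment received and can open later in the surgical arm, while sections 9.3 and 22.4 work from randomisation. Whether a complication between randomisation and surgery is to be recorded is not settled by the text.

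The size cannot be computed from the protocol. Under assumed waits of 0 to 14 days the difference is 0% to 1.9% of the 24-month window and 0% to 33% of the first six weeks. The effect on reported serious events is probably small because only related ones are reported. The direction and size of any effect on the complication comparison are unknown, because they depend on how sites read the passages, how many conservative-arm children keep their first cast, and how long surgery takes to arrange. The primary outcome and sample size are not affected.

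**What to change.** Amend section 20.1 so that safety reporting begins at randomisation in both arms and ends 24 months after randomisation. State in the guidance for the Additional Care and Site Follow Up Complications forms that complications are recorded from randomisation, regardless of whether or when the allocated treatment is given, and align the complications paragraph of section 9.3 with this.

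The cost is one sentence in section 20.1, the matching wording in section 9.3 and a line of form guidance. Sites may have a few more pre-treatment events to record. No visits, participants or changes to treatment are needed.

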20.2 Definitions

An adverse event (AE)	Any untoward occurrence in a clinical study participant. Note: An AE can therefore be any unfavourable and unintended sign (including an abnormal laboratory finding, for example), symptom or disease temporarily associated with the study procedures, whether or not considered related to the procedures.			
Related Adverse	An event that resulted from administration of any of the research			
Event	procedures			
Serious Adverse	An AE that:			
Event (SAE)	 results in death is life-threatening¹ requires hospitalisation or prolongation of existing hospitalisation results in persistent or significant disability or incapacity is a congenital anomaly or birth defect; or is otherwise considered medically significant by the Investigator² 			
Unexpected	An SAE related to the study (i.e. resulted from administration of any of the			
Related Serious	research procedures) and is unexpected (not listed in the protocol as an			
Adverse Event	expected occurrence).			

¹ If a participant was at risk of death at the time of the event; it does not refer to an event which hypothetically might have caused death if it were more severe

A distinction is drawn between serious and severe AEs. Severity is a measure of intensity whereas seriousness is defined using the criteria above. Hence, a severe AE need not necessarily be serious.

